8.5.4 Respiratory Syncytial Virus Subgroup (A or B) Determination

Nasopharyngeal swab sample(s) will be analyzed to determine whether the virus belongs to RSV subgroup A or B. Refer to the Laboratory Manual for further details.

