### 3.5 Analysis Populations

Subjects will be initially diagnosed using a local rapid antigen test. A central laboratory RT-PCR assay will be used to confirm the local results.

*Safety (SAF) Population:* All subjects who receive at least one dose of study drug. Subjects will be analyzed in the treatment group that corresponds to the study drug received during the study.

*Modified Intent-to-Treat (mITT) Population:* All randomized subjects positively diagnosed using the central RT-PCR test who receive at least one dose of assigned study drug will be included in the mITT population. The mITT population will be considered the efficacy population. Subjects will be analyzed as randomized.

*Per Protocol (PP) Population:* All subjects in the mITT population who completed 5-day treatment period and do not have major protocol deviations that may unduly influence TSS. Protocol deviations that would exclude subjects from the PP population are defined in *Section 3.8 (Protocol Deviations)*. Subjects will be analyzed as randomized.

*Pharmacokinetic (PK) Population:* All subjects receiving active study drug and having any measurable plasma concentration of study drug at any timepoint.

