### 3.14 Efficacy Analyses

All efficacy analyses will be based on mITT population unless otherwise specified.

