### 3.14.2 Secondary Efficacy Analyses

The RSV RNA viral load will be measured in nasopharyngeal swab samples by quantitative reverse transcription polymerase chain reaction (RT-qPCR) on Days 1, 3, 5, 9 and 14. Viral load values reported as TD (Target Detected, but below LLOQ) will be set to the average of LOD (limit of detection) and LLOQ (lower limit of quantification). Viral load values reported as TND (Target Not Detected, below LOD) will be set to zero. Viral load data will be transformed using a log10 scale before analyses. In case of zero value, the log transformed value will be also set as zero.

There will be two readings for both RSV A and RSV B, one from each of the two wells (i.e. A1, A2, B1, and B2). In case of any technical failure, no readings will be reported for the standard test, but a re-test will be done using a different aliquot from the same sample to produce valid results. PPD's unblinded statistician will then review the data and identify samples meeting discrepancy criteria for RSV A or RSV B. For these samples, a re-test will be performed using a different aliquot from the same sample. The discrepancy criteria for RSV A (same for RSV B) are defined as the following:

- Both A1 and A2 are numeric, and A1/A2 is  $>10$  or  $<1/10$  (i.e., one log difference);
- One of A1 and A2 is numeric, and the other one is TD or TND
- One of A1 and A2 is TD, and the other one is TND

For each sample, the final data will contain one or two sets of results.

The final RSV value (for A and B separately) for each sample will be the simple mean of the readings in original scale based on the following:

- Two readings from the only set if the final data have only one set of results.
- Two readings from the set without discrepancy if the final data have two sets of results and one set has discrepancy while the other set has no discrepancy
- Four readings from both sets if the final data have two sets of results and both sets have discrepancy
- Four readings from both sets if the final data have two sets of results and both sets have no discrepancy

Note: The readings reported as TND (target not detected) will be replaced by zero and those reported as TD (target detected) will be replaced by the average of LOD and LLOQ in the calculation of the RSV value.

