The RSV type of each subject will be determined based on the final RSV value at baseline. If the baseline of RSV A is bigger, then the RSV type is A; otherwise, it is B. The analysis of the viral load will be based on the log scale of the RSV.

The RSV RNA viral load AUC will be derived similarly as described in *Section 3.14.1*. The AUC will be calculated based on all available assessments collected on Days 1/baseline, 3, 5, 9, and 14 and the actual date/time of each assessment will be used for the calculation. For the baseline viral load (Day 1), time is set as 0. For each assessment post first dose, the actual time in days is computed as difference between the date/time of the assessment and the date/time of the first dose. The AUC is also standardized to 14 days by multiplying  $14/t_{\text{last}}$  where  $t_{\text{last}}$  is the actual time in days of the last available assessment. Additionally, the AUC from Day 1 through Day 3, the AUC from Day 1 through Day 5, and the AUC from Day 1 through Day 9 will be also derived and standardized similarly as for AUC from Day 1 through Day 14.

An ANCOVA model with treatment group and asthma/COPD status (present or absent) as factors, and the baseline RSV RNA viral load as a covariate will be performed for the RSV RNA viral load AUC from Day 1 through Day 14. Treatment groups will be compared using a type III sum-of-squares. The least-squares means, standard errors and two-sided 95% confidence intervals (CI) will be presented for individual groups and the difference between groups. The same ANCOVA analysis will be performed for the AUC from Day 1 through Day 3, from Day 1 through Day 5, and from Day 1 through Day 9.

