### 3.17 Subgroup and Covariate Analyses

TSS AUC from Day 1 through Day 14 and RSV RNA viral load AUC from Day 1 through Day 14 will be analyzed by RSV type (A or B) using the same ANCOVA analysis as described in Section 3.14.1 and Section 3.14.2, except that RSV type and treatment by RSV type interaction are added to the model.

Other subgroup analyses may be explored as allowed by data.

[REDACTED]

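### The RSV type rule labels a double-negative or tied baseline as type B without evidence for B, most visibly in the Safety Population baseline table

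*SAP*

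**What the plan says.** SAP 3.14.2 reads RSV A and RSV B separately, in two wells each, and averages the readings on the original scale into one final value per target. For that average, "The readings reported as TND (target not detected) will be replaced by zero". A target that is detected but too low to quantify (TD) takes the midpoint between LOD and LLOQ. Typing then follows: "The RSV type of each subject will be determined based on the final RSV value at baseline", by the rule "If the baseline of RSV A is bigger, then the RSV type is A; otherwise, it is B". There is no third category, and nothing is said about a missing baseline value.

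The label is used in two places.

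- **Baseline table.** SAP 3.9 lists RSV type among the baseline characteristics and summarizes it in the same way as demographics, that is, in the Safety Population. SAP 3.5 requires only one dose for that population.
- **Subgroup models.** SAP 3.17 says that the Day 1 to Day 14 AUCs for TSS and viral load "will be analyzed by RSV type (A or B) using the same ANCOVA analysis", with type and a treatment-by-type interaction added. No other subgroup variable is named in the SAP. SAP 3.14 states: "All efficacy analyses will be based on mITT population unless otherwise specified". SAP 3.5 defines mITT as "All randomized subjects positively diagnosed using the central RT-PCR test who receive at least one dose of assigned study drug".

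Protocol 8.5.4 adds that swab samples "will be analyzed to determine whether the virus belongs to RSV subgroup A or B", and leaves the method to the Laboratory Manual. The Protocol Summary makes the relation of RSV subgroup to efficacy an exploratory objective.

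**The concern.** The rule asks for evidence before it assigns A and for none before it assigns B. The plan's own substitutions produce equal values: two undetected targets both become zero. Such a subject has shown no RSV in the quantitative assay, yet would be reported as having RSV B.

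In the baseline table this would overstate the type B count. In the subgroup models, if such subjects are present, they would all sit on one side of the comparison that serves the exploratory objective. With about 70 subjects planned, the four type-by-treatment cells average at most 70/4 = 17.5, so a few default labels could move a cell mean.

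**Working it through.** **Stated figures.** The documents give no rate of tied, double-negative or missing baselines, so there is no figure on this point to reproduce. The design figure in Protocol 11.2 does reproduce: standard error = sqrt((450² + 200²)/27) = 94.8, 275/94.8 = 2.90, and unequal-variance t-test power is 0.806 at 27 per group. It is not an input here. Its totals, 54 and about 70, serve only as a range for N.

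**Step 1. Apply the rule to each baseline pattern.**

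| RSV A | RSV B | Label | Support for the label |
|---|---|---|---|
| above 0 | 0 | A | yes |
| 0 | above 0 | B | yes |
| 0 | 0 | B | none: no RSV detected |
| all TD | all TD, same limits | B | none: both detected, tied |
| missing | missing | not stated; B if coded as a plain else | none |
| present | missing | not stated; A or B depending on coding | none for B |

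In the last row, a direct SAS comparison gives A because a missing value sorts lowest, while code that requires both values before assigning A gives B. The TD tie needs equal (LOD + LLOQ)/2 for the two targets, and the documents do not give the limits.

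The re-test criteria in SAP 3.14.2 compare the two wells of one target. Two undetected wells agree with each other, so a double-negative sample does not meet those criteria.

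**Step 2. Follow these subjects into the analyses.**

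- *Baseline table.* Entry needs only a dose. The mITT definition itself allows for dosed subjects without central confirmation. If both targets are undetected at baseline, they are counted as B.
- *Subgroup models, if the central RT-PCR is the Day 1 quantitative swab.* Double-negative and missing baselines are outside mITT, so their count is 0. Only non-zero ties remain.
- *Subgroup models, if it is another test or sample.* Some double negatives could be in mITT. Protocol 8.5.2 describes a separate Day 1 confirmatory panel. SAP 3.14.2 also plans a below-LOD comparison on Day 1, which would be zero by construction under the first reading. That may be a drafting slip, because the endpoint list in SAP 2.2.2 starts at Day 3.

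**Step 3. Size, under assumptions.** Let u be the share with an undetermined baseline and p the share truly type A, taken as the same in the undetermined group.

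- Labelled B by default: N·u
- Labelled B in total: N·[(1−u)(1−p) + u]
- Truly A but labelled B: N·u·p
- Share of the B group labelled by default: u/[(1−u)(1−p) + u]
- Share of the B group truly A: u·p/[(1−u)(1−p) + u]

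With u = 0.05 and p = 0.5:

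- N = 54: 2.7 default labels in a B group of 25.65 + 2.7 = 28.35, of whom 1.35 are truly A.
- N = 70: 3.5 default labels in a B group of 33.25 + 3.5 = 36.75, of whom 1.75 are truly A.
- Either way, 2.7/28.35 = 9.5% are default labels and 1.35/28.35 = 4.8% are truly A.

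Over u from 0.02 to 0.20 and p from 0.3 to 0.7, the truly-A share runs from 0.006/0.706 = 0.8% to 0.14/0.44 = 31.8%, or 0.3 to 9.8 subjects. The width reflects the assumed ranges and says nothing about which value is likely. For a subject with no RSV at all, neither label is right, so the default-label share is the relevant one.

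**The case against.** The best defence is the population. The subgroup models run in mITT, which requires a positive central RT-PCR. If that is the Day 1 quantitative swab, the double negatives never reach the models. This stands as a conditional protection, because SAP 3.5 does not name the sample. It gives no protection to the baseline table.

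A reader might also infer that every missing baseline becomes B. The documents do not say so. The rule needs a baseline value, SAP 3.3 generally does not impute, and the label would depend on programming. In the viral load model a subject without baseline viral load drops out anyway, because it is a covariate. Missing values should also be few: the Day 1 swab must precede dosing, and technical failures are re-tested.

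Non-zero ties should be rare. They need identical averages, or both targets at TD with equal limits. Such a subject is a co-detection with no single correct type, so calling the label a misclassification goes too far.

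Finally, a reader might infer that the SAP disregards a separate laboratory subtyping. Protocol 8.5.4 does not describe its assay, and the separate A and B wells in SAP 3.14.2 may be that determination.

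**Conclusion.** The point holds as a defect in a stated rule: double-negative and exactly tied baselines are called type B with no evidence for B. The firm consequence is in the Safety Population baseline table, where a dosed subject without central confirmation can be counted as RSV B.

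The stronger reading, that the subgroup analysis is contaminated, is not supported. It depends on which central RT-PCR sample defines mITT, and on whether a defaulted subject is truly A. The size is unknown and probably small. The 4.8% above rests on an assumed 5% undetermined share and an even split, and for double negatives in the subgroup models the count may be zero. The primary TSS AUC model and the viral load AUC model contain no RSV type term. This is a minor correction.

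**What to change.** Before unblinding, replace the typing sentence in SAP 3.14.2 with a symmetric rule:

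1. Type A if baseline A exceeds baseline B.
2. Type B if baseline B exceeds baseline A.
3. Otherwise, including when a value is missing, use the Protocol 8.5.4 result from the baseline swab if it is a separate determination.
4. If that does not settle it, code the subject as undetermined.

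Show undetermined as its own row in the SAP 3.9 baseline table and omit it from the SAP 3.17 RSV-type models. Do not assign type from post-baseline samples: an antiviral may change which later samples can be typed, so typing could differ by arm and bias the interaction. State in SAP 3.5 which central RT-PCR sample defines mITT, so that the reach into the subgroup models is known.

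The cost is a few sentences and no new assays. The downside is that a few subjects may drop out of the subgroup models.

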### 3.6 Analysis Visit Windows

Study day is defined as the number of days from the date of first dose. Day 1 is the date of first dose. For assessments or events after the first dose date, study day is calculated as the date of interest minus first dose date plus 1 day. For assessments/events before the first dose date, study day is calculated as the date of interest minus first dose date.

Analysis visit windows are described in the tables below.

For vital signs and safety laboratory tests:

Analysis Visit #	Analysis Visit Label	Target Day	Derivation
1	Day 1	1	Based on nominal visit

5	Day 5	5	Based on nominal visit
14	Day 14	14	Based on nominal visit

For RSV RNA quantitation of viral load:

[figure not shown]
Analysis Visit #	Analysis Visit Label	Target Day	Derivation
1	Day 1	1	Based on nominal visit
3	Day 3	3	Based on nominal visit
5	Day 5	5	Based on nominal visit
9	Day 9	9	Based on nominal visit
14	Day 14	14	Based on nominal visit

For RSV symptom diary:

Analysis Visit #	Analysis Visit Label	Target Day	Timepoint* Assessment	Derivation
1	Day1	1	1	Study day =1
1	Day1	1	2	Study day =1
2	Day 2	2	1	Study day =2
2	Day 2	2	2	Study day =2
3	Day 3	3	1	Study day =3
3	Day 3	3	2	Study day =3
4	Day 4	4	1	Study day =4
4	Day 4	4	2	Study day =4
5	Day 5	5	1	Study day =5
5	Day 5	5	2	Study day =5
6	Day 6	6	1	Study day =6
6	Day 6	6	2	Study day =6
7	Day 7	7	1	Study day =7

7	Day 7	7	2	Study day =7
8	Day 8	8	1	Study day =8
8	Day 8	8	2	Study day =8
9	Day 9	9	1	Study day =9
9	Day 9	9	2	Study day =9
10	Day 10	10	1	Study day =10
10	Day 10	10	2	Study day =10
11	Day 11	11	1	Study day =11
11	Day 11	11	2	Study day =11
12	Day 12	12	1	Study day =12
12	Day 12	12	2	Study day =12
13	Day 13	13	1	Study day =13
13	Day 13	13	2	Study day =13
14	Day 14	14	1	Study day =14
14	Day 14	14	2	Study day =14

[figure not shown]
\* RSV symptom diary is completed twice daily by subjects and thus assigned as Timepoint 1 and 2. For Day 1, timepoint 1 corresponds to the pre-dose diary and timepoint 2 to the post-dose diary.

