The TSS AUC from Day 1 through Day 14 will be calculated using the trapezoid rule (*Matthews et al., 1990*). The AUC will require at least 2 non-missing calculated total symptom scores. Missing total symptom score data will be reviewed for potential impact, and any decisions to include subjects that fail these criteria above will be documented. The AUC will be calculated based on available individual assessments of TSS collected twice per day from Day 1 through Day 14, and the actual date/time of each assessment will be used for the calculation. For the baseline TSS, the actual time is set as 0. For each assessment post first dose, the actual time in days is computed as difference between the date/time of the assessment and the date/time of the first dose. The AUC is also standardized for 14 days by multiplying  $14/t_{last}$  where  $t_{last}$  is the actual time in days of the last available assessment. Additionally, the AUC from Day 1 through Day 3, the AUC from Day 1 through Day 5, and the AUC from Day 1 through Day 9 will be also derived and standardized similarly as for AUC from Day 1 through Day 14.

The AUC TSS from Day 1 through Day 14 will be compared between EDP-938 and placebo using an analysis of covariance (ANCOVA) model with treatment group, asthma/COPD status (present or absent) as factors and the baseline TSS as a covariate. The analysis will be performed using SAS procedure MIXED. Treatment groups will be compared using a type III sum-of-squares. The least-squares means, standard errors and two-sided 95% confidence intervals (CI) will be presented for individual groups and the difference between groups. The same ANCOVA analysis will be performed for the TSS AUC from Day 1 through Day 3, from Day 1 through Day 5 and from Day 1 through Day 9.

Descriptive statistics will be displayed for TSS and change from baseline by day and timepoint and also for average daily TSS by day and will include at a minimum the number of non-missing measurements, mean, standard deviation, median, minimum, maximum, and 95% CI for the mean.

Multiple line graphs of TSS will be produced:

- (1) Observed mean TSS  $\pm$  95% confidence interval by days 1-14 and timepoint for each treatment group
- (2) Observed mean TSS (average per day)  $\pm$  95% confidence interval by days 1-14 for each treatment group

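### The SAP measures AUC time in elapsed days but rescales to day labels, so an on-schedule Day 1–14 viral-load AUC is multiplied by 1.077 and can vary with the date of the last visit

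*SAP*

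**What the plan says.** For viral load, SAP 3.14.2 fixes the time origin ("For the baseline viral load (Day 1), time is set as 0"). After first dose, "the actual time in days is computed as difference between the date/time of the assessment and the date/time of the first dose". It then states: "The AUC is also standardized to 14 days by multiplying" 14/t_last, where t_last "is the actual time in days of the last available assessment". The AUCs for Day 1–3, 1–5 and 1–9 "will be also derived and standardized similarly as for AUC from Day 1 through Day 14", with no formula given. Subjects with complete data are not exempted.

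SAP 3.6 numbers days differently: after first dose, "study day is calculated as the date of interest minus first dose date plus 1 day". It assigns swabs by nominal visit, while 3.14.2 integrates at actual times. The schedules (Protocol Appendix 1, SAP Appendix 5.1) allow +1 day at Day 5 and ±1 day at Days 9 and 14; none is shown for Day 3.

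SAP 3.14.1 uses the same construction for the primary symptom-score AUC ("For the baseline TSS, the actual time is set as 0", then 14/t_last).

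**The concern.** The numerator of the multiplier is a day label and the denominator is elapsed time. Day k falls k − 1 days after the dose date, so the two disagree by one day even when every sample was taken on schedule. A step that looks like a correction for incomplete follow-up therefore changes complete data too, and proportionally more in the shorter windows.

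The second consequence concerns visit dates. SAP 3.14.2 sets the log10 value to zero when virus is not detected, so a cleared subject accrues no more area. The multiplier still falls as the last swab moves later, so the appointment date changes that subject's AUC although the illness did not.

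At stake are the size of the reported estimates and their intervals, the meaning of the window labels, and avoidable noise in a secondary endpoint with about 35 subjects per arm. The same rule governs the primary endpoint.

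**Working it through.** **Plan's own figure.** The documents give no value for viral-load AUC or for the multiplier, so there is nothing to reproduce on this point. The one design figure, 27 per group for 80% power on symptom-score AUC, does reproduce (80.6% by the unequal-variance noncentral t) and is not affected.

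**1. Multiplier on complete data.** With N the day label, the multiplier is N/t_last, and t_last = N − 1 on schedule. Visits are taken at whole days after the dose, so the Day 3 swab is at 48 hours.

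| Window | t_last on schedule | Multiplier | t_last allowed | Range |
|---|---|---|---|---|
| Day 1–14 | 13 | 14/13 = 1.077 | 12 to 14 | 1.167 to 1.000 |
| Day 1–9* | 8 | 9/8 = 1.125 | 7 to 9 | 1.286 to 1.000 |
| Day 1–5* | 4 | 5/4 = 1.25 | 4 to 5 | 1.25 to 1.00 |
| Day 1–3* | 2 | 3/2 = 1.50 | no window shown | 1.50 |

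*On the natural reading of the text for the shorter windows.

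For these three windows, an AUC differs by the full multiplier range only if the load is already zero at the preceding swab.

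**2. Effect on the analysis.** Multiplying every AUC by a constant c multiplies the LS means, difference, standard error and interval by c. The t statistic and percentage difference do not move. In a simulated data set with 35 per arm, c = 1.5 took the ANCOVA difference from −5.30 to −7.95 and left p at 0.0046.

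**3. Visit-date effect, Day 1–14.** The curves are assumed, since the documents give none. Swabs are at 0, 2, 4 and 8 days and t_last.

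Take a load falling linearly from 7 log10 to 0 at 8 days: 7, 5.25, 3.5, 0, 0. Its trapezoid area is 12.25 + 8.75 + 7.00 + 0 = 28.0 whatever the last visit date.

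- Last swab Day 13: 28.0 × 14/12 = 32.7
- Last swab Day 14: 28.0 × 14/13 = 30.2
- Last swab Day 15: 28.0 × 14/14 = 28.0

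The ratio of largest to smallest is 1.167. Other shapes do less:

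- 6 log10 falling linearly to 0 at 12 days: 42.0, 39.85 and 38.0, a ratio of 1.105.
- 6 log10 falling linearly to 1 at 14 days: 54.0, 51.5 and 49.0, a ratio of 1.102.
- Flat at 5: 70.0 each time, a ratio of 1.000.

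**4. Noise.** If Days 13, 14 and 15 are equally likely, the multipliers 1.167, 1.077 and 1.000 have a CV of 6.3%. At 20/60/20 the CV is 4.9%. If the between-subject CV of the AUC were 30% to 50% (assumed; the documents give none), an independent 6.3% multiplier would raise variance by 0.063² × (1 + 1/0.30²) = 4.8% to 0.063² × (1 + 1/0.50²) = 2.0%.

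**5. Labels across endpoints.** If the Day 3 evening diary is at about 2.4 days (assumed), symptom-score AUC for Day 1–3 is multiplied by 3/2.4 = 1.25 and viral-load AUC by 1.50, under one label.

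**The case against.** The best defence is that 14 × (AUC/t_last) is a time-weighted mean expressed over 14 days, and Day 1 through Day 14 does span 14 calendar days. On that view 1.077 is a convention. The rule also helps subjects who have not cleared: a flat curve's raw area is 60, 65 or 70 for a last swab on Day 13, 14 or 15, and rescaling makes all three 70.

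The second part stands: the multiplier helps flat curves and hurts cleared ones. The first part stands only for flat curves. The falling curve in step 3 has a full 14-day area of 28.0, yet on schedule it is reported as 30.2, because the added day is filled at the past average instead of the current level.

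Four stronger readings are tempting and unsupported:

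- **That the rule exaggerates significance or relative benefit.** A common factor changes neither.
- **That a 50% inflation is written into the plan.** The factor 3/t_last is inferred, and the SAP introduces the shorter windows as additional analyses. The secondary endpoint in SAP 2.2.2 is Day 1–14. Nor does the text state outright whether the raw or the standardized AUC enters the ANCOVA.
- **That every complete AUC is inflated.** A last swab on Day 15 has a multiplier of 1.00.
- **That visit dates bias the comparison.** This needs timing to differ by arm, and nothing in this randomized, double-blind plan with scheduled visits suggests a mechanism.

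**Conclusion.** The rule mixes day labels with elapsed time. The 1.077 for an on-schedule Day 1–14 viral-load AUC follows from the SAP's text, provided the standardized AUC is the one analysed. The 1.125, 1.25 and 1.50 also depend on the natural reading for the shorter windows.

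The effect is on the scale of reported estimates and intervals. The visit-date effect is at most 17% for Day 1–14, reached when load is zero by about Day 9; it was about 10% for the two slower curves tried and 0% for a flat one. As noise it is small (multiplier CV about 5–6% under assumed visit-day distributions). It is demonstrated for swabs, which are assigned by nominal visit; symptom diaries are assigned by study day.

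This does not threaten the validity of the test. It should still be corrected, because the change is cheap.

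**What to change.** Amend SAP 3.14.1 and 3.14.2 before unblinding:

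1. Define fixed horizons from first dose: 2, 4, 8 and 13 days for viral load, and a stated matching horizon for symptom score.
2. Where the window's final assessment exists, integrate to the horizon with no multiplier. Interpolate if the visit is late; carry the last value forward at most 1 day if it is early.
3. Use the same horizon in any rule kept for a missing final assessment (13/t_last, not 14/t_last).
4. Write out the shorter-window formulas and state that this AUC enters the ANCOVA.

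Changing only the numerator to 13 would restore 1.00 on schedule but leave the visit-date ratio at (13/12)/(13/14) = 1.167. The fixed horizon gives 28.0 on all three dates for the cleared curve and 65.0 for the flat one.

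Some dependence remains for intermediate curves. For 6 log10 falling to 0 at 12 days, the area to 8 days is 32.0. The remainder is 4.0 (Day 13, zero carried forward), 5.0 (Day 14), or (2 + 0.333)/2 × 5 = 5.83 (Day 15, interpolated), giving 36.0, 37.0 and 37.8. The ratio falls from 1.105 to 1.051.

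The cost is SAP wording and programming, a small interpolation and carry-forward assumption, and somewhat smaller reported AUCs.
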